3.3 CONCURRENT THERAPIES

N/A

3.4 CRITERIA FOR REMOVAL FROM TREATMENT/PROTOCOL

3.4.1 OFF TREATMENT CRITERIA:

Subjects who come off treatment will be returned to usual care for cardiac risk factors as directed by their primary physician. If they consent to continue imaging follow up, they will complete imaging as per protocol.

1. Occurrence of a clinical cardiovascular event including myocardial infarction, acute coronary syndrome, angina, heart failure, stroke or revascularization.
2. Inability to continue on study medications (adverse reaction, not wanting to adhere to the study medications)
3. Elevations of liver enzymes more than three times the upper limits of normal that persists in repeat testing and cannot be explained by other factors than statin use.
4. Myopathy defined as muscle pain with serum creatinine kinase concentrations > 1000 U/L. Any other relevant clinical or laboratory abnormality which cannot be confidently excluded as a side effect from study medications will lead to discontinuation of an individual patient from the trial.

3.4.2 OFF STUDY CRITERIA

1. Request of the patient or their personal physician.
2. Pregnancy or nursing
3. Subjects who come off study for any reason will be referred back to their personal physician.
4. Per PI discretion

4. SUPPORTIVE CARE

Study investigators and support staff will provide further consultation to participants by in-person visits, phone or electronic communication (telehealth) as needed to address participant concerns regarding study therapy or imaging evaluation.

5. DATA COLLECTION AND EVALUATION

5.1. HUMAN SPECIMEN USE, DISPOSITION, TRACKING AND STORAGE OF SAMPLES AND DATA

During the course of participating on this study, blood, tissue and data may be collected for correlative laboratory research studies. Specimens collected strictly for research purposes will not be read by a pathologist.

Biospecimen management: Specimens and their derivatives (e.g., genomic material, cell lines) will be coded and stored in conformity with DIR Policy (e.g., BSI). Coded biospecimens may be sent to collaborators outside of the NIH with IRB approval in accordance with applicable NIH and DIR Policy for sharing research resources, including an executed material transfer agreement. Biospecimens with subject personal identifiers may be sent to associate investigators and collaborators outside of the NIH only after approvals of both NHLBI and local IRBs, an executed reliance agreement with NHLBI's IRB, or an extension of the NIH's FWA through an Individual Investigator Agreement.

Data Management: The principal investigator, associate investigators, research nurses and/or a data manager will assist with the data management efforts. Data will be abstracted from Clinical Center progress notes as well as intake forms and the case report forms. Laboratory data from NIH will be reviewed using CRIS. The principal investigator, associate investigators/research nurses and/or a contracted data manager will assist with the data management efforts to ensure that data are verifiable

and evaluable. Data will be abstracted from Clinical Center progress notes as well as from progress notes forwarded from the subjects' home physician.

The PI will be responsible for overseeing entry of data into an in-house password protected electronic system and ensuring data accuracy, consistency and timeliness. Laboratory values from referring home physicians will be entered into the system. The principal investigator, associate investigators/research nurses and/or a contracted data manager will assist with the data management efforts to ensure that data are verifiable and evaluable.

Research data will be prospectively collected by authorized Investigator personnel and entered into an NHLBI, 21 CFR 11 compliant, database which will consist of the study specific set of electronic CRFs (e-CRFs) used for capturing, managing and reporting clinical research data.

The database will maintain complete data records on each research subject. Subjective and objective patient experiences during the duration of the study will be documented in the patient medical record notes. These protocol notes will serve as the primary source material from which data will be collected in the database. Any pertinent supplementary information obtained from outside laboratories, outside hospitals, radiology reports, laboratory reports, or other patient records will be used as additional sources for data collection.

We will maintain the confidentiality of identifiable private information collected in this Clinical Trial and protect the privacy of the individual human subjects. Primary data containing individually identifiable information obtained during the conduct of the protocol will be kept in secure network drives or in approved alternative sites that comply with NIH information security standards. Neither individual personal identifiers nor the key linking coded data to individuals will be released without prior IRB approval and an executed confidential disclosure agreement (CDA) or material transfer agreement (MTA). Identifiable data will not be sent outside NIH without prior IRB approval or appropriate conditions for disclosure outlined in the executed CDA or MTA.

Standard forms for patient history, labs, imaging results. Digital source documentation from CTDB (Clinical Trials Database) will be used. CTDB is a password protected secure database at the NIH Clinical Center. Complete records must be maintained on each patient, which will consist of the hospital chart with any supplementary information obtained from patient, outside laboratories, progress notes, reports, consults or tests.

The database storing the entire information set will be based on coded identification. The confidentiality and security of the data files in the computer will be maintained by ensuring password protection on all computer accounts. Protection against loss of data is essential to our data management. Quality control procedures will also include:

- 1) Assurance or the prevention of possible errors;
- 2) Assessment, or the detection of errors after they have occurred and;
- 3) Feedback, or the correction of system failures which originated the error and is necessary to avoid errors in the future. Detailed checklists are used for data collection and trial procedures.

Storage: All samples will be stored in the laboratory of [name]. Collected samples will be de-identified prior to storage in the laboratory of the principal investigator following current NHLBI DIR BSI Policy. Efforts to ensure protection of patient information include;

- Each sample is assigned a unique number.
- Vials holding patient samples are labeled with the sequential laboratory accession ID number that does not contain any personal identifier information.
- An electronic database is used to store patient information related to the coded samples
- The laboratory is located in a controlled access building and laboratory doors are kept locked. Visitors to the laboratory are required to be accompanied by laboratory staff at all times.

Hard copy records or electronic copies of documents containing patient information are kept in the locked laboratory or other controlled access locations.

Data sharing and future use of data

Research data may be shared with qualified non-collaborator recipients following publication of the primary research results after removal of PII and IRB or OHSRP approval. Future research use of data not defined in the research protocol may occur only after IRB review and approval or an exemption from the NIH Office of Human Subjects Research Protections (OHSRP). Refusal of a research subject participant to permit future use of data--other than required in the protocol or by the FDA--will be honored. Limitations in data sharing and future use of data due to contractual obligations (e.g., CRADAs) or intellectual property proceedings (such as patent filings) will be honored.

Future use of biospecimens

Following analyses of biospecimens for primary research purposes as described in the protocol, remaining samples suitable for future research must be stored in manner that conforms with DIR policy (such as BSI) or in a publicly accessible research biospecimen repository following IRB approval. Biospecimens may be destroyed only when permitted by the clinical director and approved by the IRB.

Any future research use of biospecimens not defined in the research protocol in which NHLBI investigators are engaged in research (e.g., they are undertaking research activities and hold the key that identifies research subjects) requires IRB review and approval. Coded biospecimens (NHLBI investigators hold the key that identifies research subjects) to be shared outside of NIH for future research use requires IRB review and approval (for research collaborations) or submission of a determination to OHSRP (for non-collaborative research), and an executed transfer agreement. Unlinked biospecimens (no key to identify research subjects exists) to be shared outside of NIH for future research use requires submission of a determination to OHSRP and an executed transfer agreement. There are a few types of biospecimens that do not require IRB or OHSRP approval for future research use outside of NIH, such as specimens from deceased individuals (refer to OHSRP SOP5, Appendix 1 for complete list); an executed transfer agreement is required in these special cases. Refusal of a research subject participant to allow for future use of biospecimens-other than required in the protocol or the FDA-will be honored.

Tracking: Samples will be ordered and tracked through CRIS Research Screens. Should a CRIS screen not be available, the NIH form 2803-1 will be completed and will accompany the specimen and be filed in the

medical record. Samples will not be sent outside NIH without IRB notification and an executed MTA or CTA.

End of study procedures: Samples from consenting subjects will be stored until they are no longer of scientific value. At the completion of the protocol (termination), samples and data will be maintained in a repository for future research.

Loss or destruction of samples: Should we become aware that a major breech in our plan for tracking and storage of samples has occurred, the IRB will be notified.

Loss or destruction of data: Should we become aware that a major breech in the plan to protect patient confidentiality and trial data has occurred, the clinical director and IRB will be notified.

Publication Policy: Given the research mandate of the NIH, patient data including the results of testing and responses to treatment will be entered into an NIH-authorized and controlled research database. Any future research use will occur only after appropriate human subject protection institutional approval such as prospective NIH IRB review and approval or an exemption from the NIH Office of Human Subjects Research Protection (OHSRP).

Privacy and Confidentiality: All efforts, within reason, will be made to keep subjects' protected health information (PHI) and private identifiable information (PII) private. Using or sharing ("disclosure") such data must follow federal privacy rules. Under certain circumstances, the United States Office of Human Research Protections (OHRP), The US Food and Drug Administration (FDA), and the NIH Intramural Institutional Review Board (IRB), will be able to inspect and copy confidential study-related records which identify participants by name. Therefore, absolute confidentiality cannot be guaranteed.

5.2. RESPONSE CRITERIA

Response to high-intensity therapy will be assessed according to GRCR 2013 guidelines and are expected to result in LDL levels by 50%. To be consistent with new clinical practice guidelines for lipid lowering therapy, specific lipid targets will not be used as response criteria to guide therapy.

6. STATISTICAL CONSIDERATIONS

Primary Endpoint: The primary endpoint of this study is the change in noncalcified plaque volume after 24 months.

Secondary Endpoints: In addition to the 24 months follow-up period specified for the primary endpoint, we plan to follow the patients for an extended period of 12 months to study the long term effects of the statin therapy. As a result, the patients will be followed for a total of 36 months with the first 24 months for the primary endpoint and the additional 12 months for the secondary endpoints. The secondary endpoints include:

- 1) Change in noncalcified plaque volume assessed by CCTA at the end of 36 months;
- 2) Effects of covariates including age, sex, race, body mass index and baseline plaque volume on the change of plaque volume measured by CCTA at 24 and 36 months.

- 3) The relationship of CMR T1 high signal intensity plaque and change in T1 signal by CMR over time to CCTA plaque characteristics.
- 4) (Pilot study): the relationship of coronary artery plaque by CCTA to sodium fluoride (F18-NaF) uptake using positron emission tomography (PET) scanning:
 - a. Determine if F18-NaF signal correlates with CCTA defined plaque volume and CAC score.
 - b. Determine the change in F18-NaF signal in relationship to statin therapy

Preliminary Information: One study in the literature was conducted as a pilot study with similar goals (Burgstahler et al. 2007). This pilot study investigated 22 noncalcified plaques in 12 patients before and after lipid lower therapy for 18 months. The mean patient age (61) and cardiovascular risk profile was similar to that expected in our cohort. The medication used was atorvastatin 20 mg. The mean (\pm sd) volume of all plaques was reduced by statin therapy from 0.042 ± 0.029 mL to 0.030 ± 0.014 mL ($P < 0.05$). The mean reduction of plaque volume was 0.012 mL with the standard deviation 0.017 mL.

Statistical Hypotheses: Because the study of Burgstahler et al. (2007) is based on a small sample size, we would like to consider a somewhat conservative assumption on the mean and sd for the plaque volume reduction than the preliminary information provided by this study. Specifically, we hypothesize that the patients with high intensity statin treatment will have at least 0.008 mL mean reduction of plaque volume at the end of the 24 months treatment period. Let

$$\Delta = \text{mean reduction of plaque volume at 24 months.}$$

The statistical setting is to test the null hypothesis " $H_0: \Delta=0$ " versus the two-sided alternative of " $H_1: \Delta \neq 0$ " at 0.05 significance level with 90% power. The null hypothesis suggests that the mean plaque volume reduction is the same at the beginning of the study and the end of 24 months, while the alternative suggesting changes of the mean plaque volume at the two time points. Based on the information provided in Burgstahler et al. (2007), we believe that it is reasonable to conduct a statistical test to detect an effective Δ of at least 0.008 mL under the somewhat conservative assumption that the sd of Δ is 0.03 mL.

[figure not shown]
Sample Size Justification: We plan to conduct a group sequential trial with one interim analysis when approximately half of the patients completed the 24 months follow-up. Using the Lan-DeMets O'Brien-Fleming approximate spending function, our test requires $n=151$ patients to be followed at the end of the 24 months to reach the required 0.05 significance level and 90% power. Assuming approximately 20% dropout at the 24 month time point, the number of enrolled subjects will be 190.

Interim Analysis: The interim analysis will be conducted when $n_1=76$ patients completed the 24 months follow-up period. The lower and upper stopping boundaries for the interim analysis are $Z_1=-2.96$ and 2.96 , respectively, where Z_1 is the test statistic for the statistical hypotheses H_0 and H_1 at the interim look (see Figure 1 below). The corresponding nominal p-value at this interim look is 0.0015. The study will be considered for stopping due to efficacy if the test statistic Z_1 crosses the upper bound, i.e., $Z_1 > 2.96$, while, the study will be considered for stopping due to futility if the test statistic Z_1 crosses the lower bound, i.e. $Z_1 < -2.96$. However, the DSMB will make the decision on whether the study should be stopped at the interim look.

Final Analysis: In the most like event the study is proceeded to the final stage, the final analysis for the primary endpoint will be determined by the test statistic Z_2 with all $N=151$ patients completed the 24 months follow-up. The null hypothesis H_0 of no difference of the mean plaque volume between the baseline and the 24 months will be rejected if $|Z_2| > 1.97$ (see Figure 1 below).

Software: Sample sizes and stopping boundaries of the group sequential design are computed using the R “gsDesign” package, version 3.1.3 (2015-03-09). Details of the statistical methods and theory of the design are described in C. Jennison and B. W. Turnbull (2000, “Group Sequential Methods with Applications to Clinical Trials”, Chapman and Hall/CRC, Boca Raton, FL).

Figure. Stopping boundaries with one interim look based on the Lan-DeMets O’Brien-Fleming approximate spending function.

Noncompliance and Missing Data: Given our past experience in similar clinical trials, we do not anticipate noncompliance as a major problem. However, despite the best possible effort, there are inevitably noncompliant patients and/or patients with missing data. We categorize the noncompliance and missing data into the following three situations:

- 1) **Noncompliant patients with complete follow-up examinations at baseline and 24 months:** The primary analysis of these patients, including both the interim analysis and the final analysis of the primary endpoint, will be carried out using the intent-to-treat (ITT) principle. Under the ITT principle, the observed plaque volumes at baseline and 24 months from these patients will be included in the primary analysis.
- 2) **Noncompliant patients with missing examinations at 24 months:** Since plaque volume normally does not decrease without significant intervention, we will apply the ITT principle to these patients using the approach of setting their plaque volumes at 24 months to be the same as their baseline values.
- 3) **Compliant patients with missing examination at 24 months:** We expect that only a small portion of the patients will fall into this category, since our study coordinators will give their best efforts to contact and keep track these patients. For the primary analysis, we will include these patients using the same approach as 2) by setting their plaque volumes at 24 months to be the same as their baseline values.

- 4) **Secondary analysis of the above patients:** In addition to the ITT and missing data approaches mentioned in 1)-3), our secondary analysis of the primary endpoint (change of plaque volume between baseline and 36 months) will also include: a) non-ITT approach of including only treatment compliant patients in the analysis, b) complete data approach of using only patients with observed plaque volumes in both baseline and 36 months. As a sensitivity analysis, we will compare the results obtained from a) and b) above with the primary analysis of 1)-3). This sensitivity analysis will provide useful insights into the characteristics of the patients with noncompliance and/or missing plaque volume data at 24 and 36 months.

Secondary Analysis with Subgroups and Covariates: Regression models will be considered for the analysis of secondary endpoints.

- 1) **Cross-Sectional Data:** Regression models with cross-sectional outcome and covariates, i.e. data without repeated measurements over time, will include multivariable linear and nonlinear models. Nonparametric smoothing methods, such as splines and local polynomials, will be used to explore the relationships between the outcome and covariates. The flexible ANOVA F Goodness-of-Fit tests will be used to test the adequacy of the parametric linear and nonlinear regression models.
- 2) **Longitudinal Outcome and Covariate Data:** For data including repeatedly measured outcome and/or covariates over time, we will consider the commonly used linear and nonlinear mixed effects models to explore the time trends of the outcome variables and corresponding covariate effects. Similar to the exploratory analysis with cross-sectional data, we will also consider the flexible nonparametric longitudinal regression methods, such as the time-varying coefficient models and models of functional data analysis, to evaluate the appropriateness of the parametric mixed effects models.
- 3) **For Secondary endpoint 3 (relationship of CCTA plaque to T1 CMR signal):** CMR high signal intensity plaque is postulated to represent “unstable” plaque or plaque containing hemorrhage and/ or protein. CCTA plaque characteristics that are thought to be associated with unstable plaque include spotty calcification and low density plaque. Since this aim represents an exploratory aim with the use of technologically advanced CMR imaging, the incidence of CMR T1 high signal intensity plaque is unknown. We will therefore use descriptive statistics to relate the presence or absence of T1 high signal intensity to the presence or absence of various CCTA plaque characteristics. In addition, we will determine if T1 signal changes in various plaques over the study period; if T1 signal changes (e.g. due to plaque healing), we would expect that this would be more common in the presence of unstable plaque features by CCTA. For this aim, the number of T1 high signal intensity plaques at baseline that do not show high signal at 24 months will be determined. The percentage of these plaques that demonstrated unstable CCTA plaque characteristics at baseline will be determined. Data for both the 12 and 24 month time points will be considered because at present the time course of change of high T1 signal intensity plaques is not known
- 4) **For Secondary endpoint 4 (pilot study, relationship of CCTA plaque to F18-NaF signal):** A comparison of the presence or absence of NaF signal by PET will be performed. NaF signal (with both TBR and SUVmax) will be compared across different plaque morphology and compositions defined by CCTA (for example, presence of a lipid core or calcification) in order to gain an understanding of the relationships between these two imaging modalities. Correlation between imaging findings and changes will be made with age, gender, traditional risk factors (height,

weight, hypertension, etc.), absolute values and changes in statin dose, total cholesterol, LDL, HDL, triglycerides and hematological biomarkers markers of inflammation, thrombosis and atheroprotection.

Safety Monitoring of Adverse Events: Because the statin treatment is known to be safe and involve minimal risk, we do not plan a statistical stopping rule. Any adverse events will be reported to the DSMB. Continuation or stopping of the study because of the safety reasons will be made following the recommendations of the DSMB.

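### Section 6 does not say which analysis governs the 36-month plaque endpoint, and the comparison it does prescribe changes the time point and the missing-scan rule together

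*Combined protocol and SAP*

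**What the plan says.** All of the following is in Section 6 of the combined protocol and SAP unless another place is named.

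- **Primary endpoint.** "The primary endpoint of this study is the change in noncalcified plaque volume after 24 months". The Primary Aim in Section 1 and the Design section give the same time point.
- **Secondary endpoint 1.** "Change in noncalcified plaque volume assessed by CCTA at the end of 36 months". The third year of follow-up is justified by interest in long-term effects.
- **Noncompliance and Missing Data, items 2) and 3).** A participant without a 24-month scan is kept in the analysis by "setting their plaque volumes at 24 months to be the same as their baseline values". Both items name the 24-month scan only, and item 3) is confined to the primary analysis.
- **Item 4).** This describes a secondary analysis of the primary endpoint but defines that endpoint as the change from baseline to 36 months. On top of the approaches in items 1) to 3) it lists (a) a compliant-only analysis and (b) a "complete data approach of using only patients with observed plaque volumes in both baseline and 36 months". It calls the exercise a sensitivity analysis and says that the results of (a) and (b) will be compared with the primary analysis of items 1) to 3).
- **Secondary Analysis with Subgroups and Covariates.** Regression models are to be considered for the secondary endpoints. Linear and nonlinear mixed models are to be considered for exploring time trends in repeated measurements. No model is fixed for endpoint 1.
- **Dropout.** The only figure is "Assuming approximately 20% dropout at the 24 month time point". There is none for 36 months.

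**The concern.** Item 4) does two things that do not fit together. It attaches a 36-month change to an endpoint defined at 24 months, and it sets 36-month results that leave out missing participants beside a 24-month result that counts missing participants as unchanged. A difference between the two could come from the extra year, from the missing-scan rule, or from both, and the comparison cannot tell them apart.

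The plan also leaves open which approach is the estimate of secondary endpoint 1. A participant scanned at 24 months but not at 36 could be left out (item 4b), reset to baseline (if items 1) to 3) are carried over), or kept through the observed scans (if a mixed model is used). These choices can give different answers to the question that year 3 is meant to settle, namely whether plaque regresses further, holds or regrows. Each participant receives one more CT for that answer, estimated at 2.134 rem in Section 7.5.

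**Working it through.** **Inputs from Section 6.** Effect: "at least 0.008 mL mean reduction of plaque volume at the end of the 24 months treatment period". Spread: "under the somewhat conservative assumption that the sd of Δ is 0.03 mL". Test: "at 0.05 significance level with 90% power", two-sided. Dropout: about 20% at 24 months. Enrolled: 190.

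**Step 1. Reproduce the plan's sample size.**
- One-sample normal formula: n = ((1.960 + 1.282) × 0.03 / 0.008)² = 147.8, so 148. The exact t version gives 150.
- One look at half information with Lan-DeMets O'Brien-Fleming spending gives boundaries 2.963 and 1.969 (plan: 2.96 and 1.97) and an inflation factor of 1.0034. Then 150 × 1.0034 = 150.5, so 151, as stated.
- Dropout: 151 / 0.80 = 188.75, so 189 (plan: 190).

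The plan's figures reproduce, so its effect, SD and dropout are used below.

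**Step 2. A flat third year.** Give every participant a true mean reduction of 0.008 mL at both 24 and 36 months, with missingness unrelated to outcome. Let m be the share without a scan.
- Missing set to baseline: estimate = (1 − m) × 0.008.
- Observed pairs: estimate = 0.008.

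**Step 3. The comparison as item 4) writes it.**
- 24 months, items 1) to 3), m = 0.20: 0.80 × 0.008 = 0.0064 mL.
- 36 months, observed pairs: 0.0080 mL.
- Apparent further reduction: 0.0080 − 0.0064 = 0.0016 mL, and 0.0016 / 0.0064 = 25%.
- With 39 of 190 missing (190 − 151): 0.008 × 151/190 = 0.00636 mL, and the gap is 26%.
- Standard error of the 36-month mean: 0.03/√152 = 0.00243 with 20% missing, 0.03/√133 = 0.00260 with 30% missing. The gap is 0.62 to 0.66 standard errors. It is systematic, so a larger sample would not shrink it.

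**Step 4. The baseline rule extended to 36 months.** The 36-month missing shares are assumptions.
- 20% missing: 0.0064 mL, no false trend.
- 25% missing: 0.75 × 0.008 = 0.0060 mL, −6.25% against 0.0064.
- 28.4% missing (constant dropout hazard, 1 − 0.8^1.5): 0.716 × 0.008 = 0.0057 mL, about −11%.
- 30% missing: 0.70 × 0.008 = 0.0056 mL, −12.5%.

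The mechanism is that a participant with a measured 24-month reduction who misses only month 36 is scored as fully back at baseline.

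**Step 5. The plan's own premise about missing participants.** Suppose instead that the 20% without scans truly have no reduction. The whole-cohort mean is then 0.80 × 0.008 + 0.20 × 0 = 0.0064 mL at both times. Observed pairs at 36 months in the remaining 80% still give 0.0080 mL. The false trend of Step 3 does not depend on crediting dropouts with a benefit.

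**The case against.** The strongest case on the other side has five parts.

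- **A reader might infer that the plan has no rule at all for a missing 36-month scan.** The documents do not support that. Item 4b names the 36-month change and leaves such participants out. Mixed models are also listed and could use every observed scan without resetting any. What stands is that several approaches are on offer and none is designated.
- **A reader might take 20% or more missing at 36 months as a plan figure.** It is not. The 20% is stated for 24 months, and Section 3.4.1 lets participants who stop treatment continue imaging. Any 36-month share is an assumption.
- **The distortions are modest and conditional.** The false regression is below one standard error, and the false regrowth needs further loss after month 24 (0.0008 mL at 30% missing, about 0.3 standard errors). No test of the change from 24 to 36 months is specified. This is correct and limits the weight of the point.
- **Item 4) calls the comparison a sensitivity analysis.** It does, but a sensitivity analysis of a 24-month endpoint should vary one thing at a time, and this one also moves the time point. Observed pairs at both 24 and 36 months in the same participants would show no false trend under Step 2, but the plan does not ask for that.
- **A mixed model will not reconcile the 36-month figure with the primary result.** In the Step 2 scenario it gives about 0.0080 mL at both times, while the primary figure stays at 0.0064 mL. That stands, so the fix needs a rule against reading those two figures as a trend.

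**Conclusion.** The point holds as a defect in how the 36-month analysis is specified. Item 4) mislabels a 36-month change as the primary endpoint, does not say which approach governs secondary endpoint 1, and prescribes a comparison in which time point and missing-data rule change together.

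On the plan's effect and 24-month dropout, with no true change in year 3, that comparison shows a false further regression of 0.0016 mL (25%, about 0.6 standard errors of the 36-month mean). Carrying the baseline rule to month 36 instead shows a false regrowth of about 6% to 12.5% if 25% to 30% are missing by then, and none if missingness stays at 20%. These sizes rest on a constant true effect among those scanned and on assumed 36-month missing shares.

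A reader might infer that the primary conclusion is at risk. The documents do not support that: the 24-month test, its boundaries and the sample size are untouched, and this point does not judge the merits of the 24-month rule. What is at stake is the reading of the long-term result.

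**What to change.** In Section 6:

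1. Correct the 24/36-month label in item 4) of Noncompliance and Missing Data, so that the compliant-only and complete-data sensitivity analyses of the primary endpoint use 24-month data.
2. State that secondary endpoint 1 is estimated from one repeated-measures mixed model fitted to all observed 0, 12, 24 and 36-month volumes, without resetting missing volumes to baseline.
3. Whenever 24 and 36 months are compared, take both means from that model. Label its 24-month figure as distinct from the primary intention-to-treat result, and state that the 36-month figure is not to be read against the baseline-filled primary figure as a trend.
4. Keep the observed-pairs 36-month analysis as a sensitivity analysis.

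The cost is wording and one model from a class that Section 6 already lists, on scans already scheduled in Appendix A. The downsides are a missing-at-random assumption and a second 24-month figure that must be labelled. If those who leave have truly lost the benefit, as in Step 5, the model would overstate the whole-cohort mean at both times, so the assumption should be stated alongside the result.
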